Appendix 1 - SPIRIT 2013 checklist

Section/item	Item	Description	Page
Administrative information			
Title	1	Descriptive title identifying the study design, population, interventions, and, if applicable, trial acronym	1
Trial registration	2a	Trial identifier and registry name. If not yet registered, name of intended registry	4
	2b	All items from the World Health Organization Trial Registration Data Set	4
Protocol version	3	Date and version identifier	6
Funding	4	Sources and types of financial, material, and other support	1
Roles and responsibilities	5a	Names, affiliations, and roles of protocol contributors	1,33
	5b	Name and contact information for the trial sponsor	1
	5c	Role of study sponsor and funders, if any, in study design; collection, management, analysis, and interpretation of data; writing of the report; and the decision to submit the report for publication, including whether they will have ultimate authority over any of these activities	1
	5d	Composition, roles, and responsibilities of the coordinating centre, steering committee, endpoint adjudication committee, data management team, and other individuals or groups overseeing the trial, if applicable (see Item 21a for data monitoring committee)	16,17
Introduction			
Background and rationale	6a	Description of research question and justification for undertaking the trial, including summary of relevant studies (published and unpublished) examining benefits and harms for each intervention	5,6
	6b	Explanation for choice of comparators	5
Objectives	7	Specific objectives or hypotheses	6,7
Trial design	8	Description of trial design including type of trial (eg, parallel group, crossover, factorial, single group), allocation ratio, and framework (eg, superiority, equivalence, noninferiority, exploratory)	6,9
Methods: participants, interventions, and outcomes			
Study setting	9	Description of study settings (eg, community clinic, academic hospital) and list of countries where data will be collected. Reference to where list of study sites can be obtained	6
Eligibility criteria	10	Inclusion and exclusion criteria for participants. If applicable, eligibility criteria for study centres and individuals who will perform the interventions (eg, surgeons, psychotherapists)	7,8,9
Interventions	11a	Interventions for each group with sufficient detail to allow replication, including how and when they will be administered	10
	11b	Criteria for discontinuing or modifying allocated interventions for a given trial participant (eg, drug dose change in response to harms, participant request, or improving/worsening disease)	11,12
	11c	Strategies to improve adherence to intervention protocols, and any procedures for monitoring adherence (eg, drug tablet return, laboratory tests)	10,11,16,17
	11d	Relevant concomitant care and interventions that are permitted or prohibited during the trial	10,11,12
Outcomes	12	Primary, secondary, and other outcomes, including the specific measurement variable (eg, systolic blood pressure), analysis metric (eg, change from baseline, final value, time to event), method of aggregation (eg, median, proportion), and time point for each outcome. Explanation of the clinical relevance of chosen efficacy and harm outcomes is strongly recommended	6,7,13

Participant timeline	13	Time schedule of enrolment, interventions (including any run-ins and washouts), assessments, and visits for participants. A schematic diagram is highly recommended (see Figure)	Figure 1
Sample size	14	Estimated number of participants needed to achieve study objectives and how it was determined, including clinical and statistical assumptions supporting any sample size calculations	13,14
Recruitment	15	Strategies for achieving adequate participant enrolment to reach target sample size	7,8,9
Methods: Assignment of interventions (for controlled trials)			
Allocation			
Sequence generation	16a	Method of generating the allocation sequence (eg, computer-generated random numbers), and list of any factors for stratification. To reduce predictability of a random sequence, details of any planned restriction (eg, blocking) should be provided in a separate document that is unavailable to those who enrol participants or assign interventions	9
Allocation concealment mechanism	16b	Mechanism of implementing the allocation sequence (eg, central telephone; sequentially numbered, opaque, sealed envelopes), describing any steps to conceal the sequence until interventions are assigned	9
Implementation	16c	Who will generate the allocation sequence, who will enrol participants, and who will assign participants to interventions	9,10
Blinding (masking)	17a	Who will be blinded after assignment to interventions (eg, trial participants, care providers, outcome assessors, data analysts), and how	10
	17b	If blinded, circumstances under which unblinding is permissible, and procedure for revealing a participant's allocated intervention during the trial	N/A
Methods: Data collection, management, and analysis			
Data collection methods	18a	Plans for assessment and collection of outcome, baseline, and other trial data, including any related processes to promote data quality (eg, duplicate measurements, training of assessors) and a description of study instruments (eg, questionnaires, laboratory tests) along with their reliability and validity, if known. Reference to where data collection forms can be found, if not in the protocol	12,13,16,17
	18b	Plans to promote participant retention and complete follow-up, including list of any outcome data to be collected for participants who discontinue or deviate from intervention protocols	12,13,16,17
Data management	19	Plans for data entry, coding, security, and storage, including any related processes to promote data quality (eg, double data entry; range checks for data values). Reference to where details of data management procedures can be found, if not in the protocol	12,13,16,17
Statistical methods	20a	Statistical methods for analysing primary and secondary outcomes. Reference to where other details of the statistical analysis plan can be found, if not in the protocol	14,15
	20b	Methods for any additional analyses (eg, subgroup and adjusted analyses)	15,16
	20c	Definition of analysis population relating to protocol non-adherence (eg, as randomised analysis), and any statistical methods to handle missing data (eg, multiple imputation)	14,15,16
Methods: Monitoring			
Data monitoring	21a	Composition of data monitoring committee (DMC); summary of its role and reporting structure; statement of whether it is independent from the sponsor and competing interests; and reference to where further details about its charter can be found, if not in the protocol. Alternatively, an explanation of why a DMC is not needed	16,17
	21b	Description of any interim analyses and stopping guidelines, including who will have access to these interim results and make the final decision to terminate the trial	14
Harms	22	Plans for collecting, assessing, reporting, and managing solicited and spontaneously reported adverse events and other unintended effects of trial interventions or trial conduct	11
Auditing	23	Frequency and procedures for auditing trial conduct, if any, and whether the process will be independent from investigators and the sponsor	NA
Ethics and dissemination			

COVID-19-associated ARDS treated with DEXamethasone

Research ethics approval	24	Plans for seeking research ethics committee/institutional review board (REC/IRB) approval	17,18
Protocol amendments	25	Plans for communicating important protocol modifications (eg, changes to eligibility criteria, outcomes, analyses) to relevant parties (eg, investigators, REC/IRBs, trial participants, trial registries, journals, regulators)	17,18
Consent or assent	26a	Who will obtain informed consent or assent from potential trial participants or authorized surrogates, and how (see Item 32)	17
	26b	Additional consent provisions for collection and use of participant data and biological specimens in ancillary studies, if applicable	NA
Confidentiality	27	How personal information about potential and enrolled participants will be collected, shared, and maintained in order to protect confidentiality before, during, and after the trial	12,13
Declaration of interests	28	Financial and other competing interests for principal investigators for the overall trial and each study site	19
Access to data	29	Statement of who will have access to the final trial dataset, and disclosure of contractual agreements that limit such access for investigators	13
Ancillary and post-trial care	30	Provisions, if any, for ancillary and post-trial care, and for compensation to those who suffer harm from trial participation	NA
Dissemination policy	31a	Plans for investigators and sponsor to communicate trial results to participants, healthcare professionals, the public, and other relevant groups (eg, via publication, reporting in results databases, or other data sharing arrangements), including any publication restrictions	17,18
	31b	Authorship eligibility guidelines and any intended use of professional writers	18
	31c	Plans, if any, for granting public access to the full protocol, participant-level dataset, and statistical code	13,17,18
Appendices			
Informed consent materials	32	Model consent form and other related documentation given to participants and authorised surrogates	NA, per Brazilian law
Biological specimens	33	Plans for collection, laboratory evaluation, and storage of biological specimens for genetic or molecular analysis in the current trial and for future use in ancillary studies, if applicable	NA

Appendix 3 - Statistical Analysis Plan (SAP) Version 2.0

Sample size and power

There is a lack of reliable data available in patients with ARDS due to COVID-19 to allow an accurate sample size calculation. We therefore used data from a randomized controlled trial in non-COVID-19 ARDS patients¹, a well-designed multicenter trial that is representative of ARDS outcomes in Brazil, to calculate the sample size. It was assumed a mean of ventilator-free days (VFD) at 28 days of 8 days \pm 9 days (standard deviation) in the control group. With a two-sided type I error of 0.05 and power of 80% to identify a difference in three days free of mechanical ventilation between groups, a sample size of 290 patients would be needed. However, in the end of May 2020, before the first interim analysis, after discussing the protocol with the Data Monitoring Committee (DMC), the Steering Committee decided to increase the sample size based on the following rationale: Given the uncertainty regarding the normality of distribution of VFD, based on the Pitman Asymptotic Relative Efficiency², the sample size should be increased by 15% to preserve study power coupled with a 4% increase considering possible lost to follow-up and withdrawal of consent. Therefore, a final sample size of 350 patients is needed.

Also, due to the lack of data about ventilator free days in COVID-19 patients, the sample size will be updated using the pooled standard deviation of ventilator free days of the first interim analysis, unless by the time of the first interim analysis all patients have been recruited.

The minimal clinically important difference of three days for VFD was chosen based on other trials^{3 4} along with what is perceived as a significant improvement to the in-hospital complications, costs, and intensive care unit availability, especially in countries with limited resources.

Interim analysis

Two interim analyses are planned for safety and efficacy evaluation, after 96 patients and 234 patients with the complete follow up to the primary outcome. Since the recruitment rate for the study is expected to increase giving the increase in number of cases of COVID-19 in Brazil it is possible that by the time all the patients for the second interim analysis have completed the follow-up for the primary outcome, the entire sample has already been recruited. Therefore, in this specific situation, the second interim analysis will be cancelled.

We will use the Haybittle–Peto boundary stopping rule for both safety and efficacy based on the evidence of significant differences between intervention or control group regarding ventilator free days at day 28, mortality or adverse events. The stopping rule for safety will be a p-value <0.01 and for efficacy p-value <0.001 . The Haybittle–Peto boundary is a conservative stopping rule at interim analysis that has minimal impact in increasing type I error in two-arm trials⁵. We will not adjust the final tests for sequential analysis. The interim analyses will be performed by an external and independent DMC.

Basic reporting principles:

The baseline characteristics of the patients will be displayed as the supplementary table 1 (**Table 1S**):

Table 1S - Baseline characteristics of included patients

	Dexamethasone (Dex.) n = xxx	Control (Cont.) n = xxx
Age, mean (SD)	xx.x ± xx.x	xx.x ± xx.x
Female sex, N (%)	xx.x (xx.x)	xx.x (xx.x)
SAPS3 score, mean (SD)	xx.x (xx.x)	xx.x (xx.x)
Number of non-pulmonary organ failures, median [IQR]	x.xx [x.xx - x.xx]	x.xx [x.xx - x.xx]
Time since onset of symptoms, median [IQR], days	x.xx [x.xx - x.xx]	x.xx [x.xx - x.xx]
Days intubated prior to randomization, median [IQR]	x.xx [x.xx - x.xx]	x.xx [x.xx - x.xx]
COVID-19, N (%)		
Positive	xx.x (xx.x)	xx.x (xx.x)
Negative	xx.x (xx.x)	xx.x (xx.x)
In analysis	xx.x (xx.x)	xx.x (xx.x)
Not collected/unavailable	xx.x (xx.x)	xx.x (xx.x)
Comorbidities, N (%)		
Hypertension	xx.x (xx.x)	xx.x (xx.x)
Diabetes	xx.x (xx.x)	xx.x (xx.x)
Former smoker	xx.x (xx.x)	xx.x (xx.x)
Active smoker	xx.x (xx.x)	xx.x (xx.x)
Obesity	xx.x (xx.x)	xx.x (xx.x)
Solid tumor	xx.x (xx.x)	xx.x (xx.x)
Hematologic malignancy	xx.x (xx.x)	xx.x (xx.x)
Heart failure	xx.x (xx.x)	xx.x (xx.x)
COPD	xx.x (xx.x)	xx.x (xx.x)
AIDS	xx.x (xx.x)	xx.x (xx.x)
Chronic renal failure	xx.x (xx.x)	xx.x (xx.x)
Chronic dialysis	xx.x (xx.x)	xx.x (xx.x)
Cirrhosis	xx.x (xx.x)	xx.x (xx.x)
Asthma	xx.x (xx.x)	xx.x (xx.x)
Neuromuscular disease	xx.x (xx.x)	xx.x (xx.x)
Previous MI	xx.x (xx.x)	xx.x (xx.x)
Clinical characteristics		
Systolic BP, mmHg, mean (SD)	xx.x ± xx.x	xx.x ± xx.x
Diastolic BP, mmHg, mean (SD)	xx.x ± xx.x	xx.x ± xx.x
HR, bpm, mean (SD)	xx.x ± xx.x	xx.x ± xx.x
SpO ₂ , %, mean (SD)	xx.x ± xx.x	xx.x ± xx.x
HScore ≥169, N ₀ (%)	xx.x (xx.x)	xx.x (xx.x)
Respiratory measures (mean, SD)		
PaO ₂ /FiO ₂	xx.x ± xx.x	xx.x ± xx.x
Tidal volume, mL/kg predicted body weight	xx.x ± xx.x	xx.x ± xx.x
Plateau airway pressure (cmH ₂ O)	xx.x ± xx.x	xx.x ± xx.x
Minute ventilation, L/min	xx.x ± xx.x	xx.x ± xx.x
Respiratory rate, breaths/min	xx.x ± xx.x	xx.x ± xx.x
Driving pressure, cmH ₂ O	xx.x ± xx.x	xx.x ± xx.x
Positive end expiratory pressure, cmH ₂ O	xx.x ± xx.x	xx.x ± xx.x
Respiratory system static compliance, ml/cmH ₂ O	xx.x ± xx.x	xx.x ± xx.x
Intravenous sedation, N (%)		
Richmond Agitation Sedation Scale, median [IQR]	x.xx [x.xx - x.xx]	x.xx [x.xx - x.xx]
Treatment during study period, N (%)		
Vasopressors	xx.x (xx.x)	xx.x (xx.x)
Renal replacement therapy	xx.x (xx.x)	xx.x (xx.x)
Use of neuromuscular blocking agents	xx.x (xx.x)	xx.x (xx.x)
ECMO	xx.x (xx.x)	xx.x (xx.x)

Prone position	xx.x (xx.x)	xx.x (xx.x)
Blood Sample		
Creatinine, mg/dL, mean (SD)	xx.x ± xx.x	xx.x ± xx.x
D-dimer, ng/dL, mean (SD)	xx.x ± xx.x	xx.x ± xx.x
Hemoglobin, g/dL, mean (SD)	xx.x ± xx.x	xx.x ± xx.x
Total leucocyte count, µg/mL, median [IQR]	x.xx [x.xx - x.xx]	x.xx [x.xx - x.xx]
Platelets, /mm ³ , mean (SD)	xx.x ± xx.x	xx.x ± xx.x
Lymphocytes, µg/mL, median [IQR]	x.xx [x.xx - x.xx]	x.xx [x.xx - x.xx]
Lactate (mg/dL)	xx.x ± xx.x	xx.x ± xx.x
Troponin, median [IQR]	x.xx [x.xx - x.xx]	x.xx [x.xx - x.xx]
Additional Medication, N (%)		
Hydroxychloroquine	xx.x (xx.x)	xx.x (xx.x)
Azithromycin	xx.x (xx.x)	xx.x (xx.x)
Other antibiotics	xx.x (xx.x)	xx.x (xx.x)
Oseltamivir	xx.x (xx.x)	xx.x (xx.x)
Lopinavir+Ritonavir	xx.x (xx.x)	xx.x (xx.x)
Use of corticosteroids before randomization, N ₀ (%)	xx.x (xx.x)	xx.x (xx.x)

The main analysis study population will comprise all patients who have been randomized (intention-to-treat population), using the group allocated as variable, regardless of the medication administered.

The primary objective is to evaluate the effectiveness of early intravenous (IV) dexamethasone administration in ventilator-free days at 28 days after randomization, defined as alive and free from mechanical ventilation in adult patients with moderate or severe ARDS due to confirmed or probable SARS-CoV2 infection. Patients discharged from the hospital alive before 28 days will be considered alive and free from mechanical ventilation at day 28. Number of days free from mechanical ventilation will be presented as mean and standard deviation. The treatment effect will be presented as mean difference, with 95% confidence interval and P-value. We will use a generalized linear model with beta-binomial distribution or zero/one inflated beta distribution, with center as random effect and adjusted for age, corticosteroid use before randomization and PaO₂/FiO₂ ratio.

All-cause mortality rates at 28 days will be analyzed using a mixed Cox model, with centers as random effects (frailty model). The treatment effect on SOFA Score 48h, 72h, and 7 days after randomization will be analyzed by a linear mixed model with centers as random effects. For the clinical status of patients, an ordinal logistic regression will be used. The results will be presented as a proportional odds ratio comparing two combinations: Intervention versus Control. The probability ratios will be derived from a mixed logistic regression of proportional probabilities adjusted for age and PaO₂/FiO₂ ratio, with random intercepts for the center. The cumulative ordinal scores will be presented separately, as well as the main secondary results. Each odds ratio will be estimated using mixed logistic regression. The same models will be used to compare the effects of treatment on the follow-up. In case of the proportional odds assumption is not met, categories of the Ordinal scale 1-4 will be grouped as a single category for the analysis. All secondary outcomes are exploratory and no adjustment for multiple testing will be made.

Adverse events will be expressed as counts and percentages and compared between groups using the Chi-square test. The main results will be displayed as the supplementary table 2 (**Table 2S**). The significance level for all analyses will be 0.05. There will be no adjustment for multiple testing. All analyses will be performed using the R software⁶ (R Core Team, Vienna, Austria, 2020).

Table 2S - Main results presentation

Outcomes	Dex.	Cont.	Treatment effect	
	n = xxx	n = xxx	Dex. versus Cont. [IC95%]	p valor
Primary outcome				
Ventilator free days from 1 to 28 d, mean (SD)	xx.x ± xx.x	xx.x ± xx.x	x.xx [x.xx; x.xx]	x.xx
Secondary outcomes				
Clinical status at day 15, N (%)				
Category 1 - 5 versus 6 (alive vs dead)	x.xx (x.xx)	x.xx (x.xx)	x.xx [x.xx; x.xx]	x.xx
Category 1 - 4 versus 5 - 6	x.xx (x.xx)	x.xx (x.xx)	x.xx [x.xx; x.xx]	x.xx
Category 1 - 3 versus 4 - 6	x.xx (x.xx)	x.xx (x.xx)	x.xx [x.xx; x.xx]	x.xx
Category 1 - 2 versus 3 - 6	x.xx (x.xx)	x.xx (x.xx)	x.xx [x.xx; x.xx]	x.xx
Category 1 versus 2 to 6 (at home versus hospital or dead)	x.xx (x.xx)	x.xx (x.xx)	x.xx [x.xx; x.xx]	x.xx
All-cause mortality at 28 days	x.xx (x.xx)	x.xx (x.xx)	x.xx [x.xx; x.xx]	x.xx
Number of days of MV from 1 to 28 d	x.xx (x.xx)	x.xx (x.xx)	x.xx [x.xx; x.xx]	x.xx
ICU free days at 28 days	x.xx (x.xx)	x.xx (x.xx)	x.xx [x.xx; x.xx]	x.xx
SOFA scores				
48 hours	x.xx (x.xx)	x.xx (x.xx)	x.xx [x.xx; x.xx]	x.xx
72 hours	x.xx (x.xx)	x.xx (x.xx)	x.xx [x.xx; x.xx]	x.xx
7 days	x.xx (x.xx)	x.xx (x.xx)	x.xx [x.xx; x.xx]	x.xx
Adverse events				
New diagnosis of infection until day 28, N (%)	x.xx (x.xx)	x.xx (x.xx)	x.xx [x.xx; x.xx]	x.xx
Insulin use for hyperglycemia, N (%)	x.xx (x.xx)	x.xx (x.xx)	x.xx [x.xx; x.xx]	x.xx

Sensitivity analyses

We plan to perform analyses to assess treatment effects on the primary and secondary outcomes considering only patients that received the proposed treatment in the intervention group and patients that not received corticosteroids in the control group (per protocol analysis). Additionally, we will also perform sensitivity analysis for the primary outcome in the following groups:

1. Confirmed COVID-19 infection
2. Confirmed and probable COVID-19 infection
3. Patients which received corticosteroids and patients which did not received corticosteroids (as treated analysis)
4. Patients which received the proposed treatment in the intervention group and patients that not received corticosteroids in the control group (Per protocol analysis)

Subgroup analyses

Will also perform subgroup analysis adding an interaction parameter with group in the main model for (Table 3S):

1. Age, years (< 60 and ≥ 60)
2. PaO₂/FiO₂ ratio, mmHg (≤ 100 and >100)
3. SAPS3, points (< 50 and ≥ 50)
4. Duration of symptoms at randomization, days (≤ 7 and > 7)
5. Duration of moderate / severe ARDS to randomization, hours (≤ 24 hours and > 24 hours to 48 hours)
6. Position at randomization; (prone or supine)
7. HScore (≥ 169 and < 169)
8. Use of corticosteroids before randomization
9. Use of vasopressors at randomization

Finally, the ordinal score (secondary outcome) will be available daily for each patient up to 15 days. These results will be presented in an alluvial graph for each arm. The conditional probabilities of change in stages (1 to 6) will be estimated via Bayesian Networks to better describe the time when the intervention can change the distribution of the score or estimate the probability of discharge. For example, Bayesian networks allow estimating the probability of discharge on day 6 if the patient is without oxygenation support on day 5. We plan to present this independent manuscript analysis with and report transition probabilities and relative risk (with confidence intervals obtained through bootstrap techniques) for relevant scenarios.

Table 3S - Effect of dexamethasone vs control on ventilator free days according to subgroups

Subgroups	Dex.	Cont.	Treatment Effect	
	n = xxx	n = xxx	HR [IC95%]	p valor
Age				
< 60 years	x.xx (x.xx)	x.xx (x.xx)	x.xx [x.xx; x.xx]	x.xx
≥ 60 years	x.xx (x.xx)	x.xx (x.xx)	x.xx [x.xx; x.xx]	x.xx
PaO₂/FiO₂				
≤ 100mmHg	x.xx (x.xx)	x.xx (x.xx)	x.xx [x.xx; x.xx]	x.xx
> 100mmHg	x.xx (x.xx)	x.xx (x.xx)	x.xx [x.xx; x.xx]	x.xx
SAPS 3				
< 50	x.xx (x.xx)	x.xx (x.xx)	x.xx [x.xx; x.xx]	x.xx
≥ 50	x.xx (x.xx)	x.xx (x.xx)	x.xx [x.xx; x.xx]	x.xx
Duration of symptoms at randomization, d				
≤ 7	x.xx (x.xx)	x.xx (x.xx)	x.xx [x.xx; x.xx]	x.xx
> 7	x.xx (x.xx)	x.xx (x.xx)	x.xx [x.xx; x.xx]	x.xx
Duration of moderate / severe ARDS to randomization, h				
≤ 24	x.xx (x.xx)	x.xx (x.xx)	x.xx [x.xx; x.xx]	x.xx
> 24 to 48	x.xx (x.xx)	x.xx (x.xx)	x.xx [x.xx; x.xx]	x.xx
Position at randomization				
Supine	x.xx (x.xx)	x.xx (x.xx)	x.xx [x.xx; x.xx]	x.xx
Prone	x.xx (x.xx)	x.xx (x.xx)	x.xx [x.xx; x.xx]	x.xx
HScore				
< 169	x.xx (x.xx)	x.xx (x.xx)	x.xx [x.xx; x.xx]	x.xx
≥ 169	x.xx (x.xx)	x.xx (x.xx)	x.xx [x.xx; x.xx]	x.xx
Use of corticosteroids before randomization				
Yes	x.xx (x.xx)	x.xx (x.xx)	x.xx [x.xx; x.xx]	x.xx
No	x.xx (x.xx)	x.xx (x.xx)	x.xx [x.xx; x.xx]	x.xx
Use of vasopressors at randomization				
Yes	x.xx (x.xx)	x.xx (x.xx)	x.xx [x.xx; x.xx]	x.xx
No	x.xx (x.xx)	x.xx (x.xx)	x.xx [x.xx; x.xx]	x.xx

Treatment adherence report

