- Patients who did use corticosteroids during hospital stay for periods equal or greater than two days
- Use of immunosuppressive drugs
- Cytotoxic chemotherapy in the past 21 days
- Neutropenia due to hematological or solid malignancies with bone marrow invasion
- Patient is expected to die in the next 24 hours
- Consent refusal for participating in the trial

Study protocol

Randomization and allocation concealment

Patients are eligible for enrolment if all the inclusion criteria and none of the exclusion criteria are met. Patients are being randomized in a 1:1 ratio to one of the two groups (Figure 1): standard treatment plus dexamethasone (intervention group) and standard treatment without dexamethasone (control group). The randomization list is generated by an independent statistician in random blocks of 2 and 4 in order to preserve the allocation concealment and is stratified by center. Randomization is performed by an online web-based central, available 24 hours a day. The group treatment is disclosed to the investigator only after all information regarding patient enrolment is recorded in the online system. Patients are screened for enrolment by the principal investigator and the research team at each study center.

Blinding

This is an open-label trial where the investigators, caregivers and patients are not blinded regarding the intervention. All statistical analyses will be performed in a blinded manner with respect to group allocation.

Trial intervention and treatment strategy

Each ICU enrolling patients in the trial are encouraged to follow the best practice guidelines and their institutional protocol for the care of critically ill patients with COVID-19. Laboratory testing, hemodynamic management, ventilatory strategy, antibiotics usage, venous thromboembolism and stress ulcer prophylaxis, along with all other ICU interventions are left at the discretion of the ICU team for both intervention and control group.

Patients in the intervention group are receiving after randomization dexamethasone 20mg intravenously once daily for 5 days, followed by dexamethasone 10mg intravenously once daily for additional 5 days or until ICU discharge, whichever occurs first. Patients in the control group are not receiving dexamethasone.

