Adherence to protocol and corticosteroids use in both groups is accessed daily. The use of corticosteroids in the control group is not forbidden since critically ill patients might have another

indication for corticosteroid use during their ICU stay. However, any use of corticosteroids for treating ARDS and or refractory hypoxemia in the control group is considered protocol deviation. Changes in dosage of dexamethasone or early interruption in the intervention group will also be considered protocol deviation.

If during the trial the patient is deemed to not have COVID-19 infection, which is defined by a negative laboratory tests along with negative evaluation by the Adjudication Committee, the study drug will be stopped, data on these patients will be collected until day 28 and will be included in the final analysis. However, giving the epidemiological context and inclusion criteria, it is expected that only a minority of patients will be in this group.

All centers will receive an initial training session before initiating recruitment to ensure consistency of the study procedures and data collection.

Data collection and management

Unidentified patient data will be collected through an electronic online data capture tool (REDCap).^(22,23) Demographic and baseline data, height, Simplified Acute Physiology Score (SAPS) 3, use of corticosteroids prior the randomization, and the HScore for diagnosis of secondary hemophagocytic lymphohistiocytosis (Table 3) are collected for all patients. The SOFA score is collected on days 1, 2, 3 and 7. Data from gas exchange, lung mechanics, hemodynamic, laboratory data, use of neuromuscular blocking agents, prone positioning and use of ECMO are collected prior randomization and until day 14.

The use of mechanical ventilation or any other ventilation/oxygen support (high flow nasal cannula, non-invasive ventilation, use of supplementary oxygen) and data on the 6-point Ordinal Scale (Table 1) are collected daily until day 28 or until hospital discharge whichever comes first. Vital status at ICU and hospital discharge and any other relevant clinical data such as nosocomial infections, insulin use for glycemic control, antibiotic use, and other therapies for COVID-19 (hydroxychloroquine, chloroquine and azithromycin) are collected.

Data on mechanical ventilation are collected in specific forms with data on date and time of initiation and discontinuation of therapy.

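### The primary ventilator-free-day model omits SAPS 3, a baseline score planned for every patient; adding it is a cheap change that may gain a little precision

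*Combined protocol and SAP*

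**What the plan says.** Three places describe the primary model, and they agree: the protocol under Statistical methods, the SAP (Appendix 3) under Basic reporting principles, and the DMC charter (Appendix 4) under the primary outcome analysis. It is a beta-binomial or zero/one inflated beta model "with center as random effect and adjusted for age, corticosteroid use before randomization and" PaO₂/FiO₂ ratio, and the effect is reported as a mean difference in days. None of the three gives a reason for this covariate set.

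SAPS 3 is planned data. The protocol's Data collection and management section lists "Demographic and baseline data, height, Simplified Acute Physiology Score (SAPS) 3, use of corticosteroids prior the randomization" among the items recorded for every patient. The score then has two uses. Table 1S shows its mean and SD by arm, and the SAP's Subgroup analyses add it to the main model as an interaction, coded "SAPS3, points (< 50 and ≥ 50". None of the listed sensitivity analyses changes the covariates.

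Two other features matter. The protocol's VFD definition gives zero days to anyone dead at day 28. Randomization is stratified by center only.

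**The concern.** Because every death scores zero, VFD is partly a mortality endpoint. The model adjusts for age, earlier steroid exposure and lung injury, but for no general measure of acute physiological severity. Any variance that SAPS 3 explains beyond the present covariates stays in the residual of the one confirmatory test. Stratifying by center does not balance severity between arms, so a chance difference in SAPS 3 also passes into the estimate. At stake is some precision in the primary comparison, recoverable from data already planned for the case report form.

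**Working it through.** **Inputs from the documents.** Control SD 9 days, difference 3 days, two-sided 5% error, 80% power, 1:1 allocation, 290 patients raised to 350, 51 centers (protocol Methods and Sample size calculation; SAP Sample size and power).

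**Input not in the documents.** The partial R² of SAPS 3 for VFD, given age, prior corticosteroids and PaO₂/FiO₂. I take 0 to 0.10 as an assumption.

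**Step 1: the plan's own figure.** n per arm = 2 × 9² × (1.960 + 0.842)² / 3² = 141.3, so 142 per arm and 284 in total (286 by the t-test). The SAP says "to identify a difference in three days free of mechanical ventilation between groups, a sample size of 290 patients would be needed"; 145 per arm gives 81.0% power. It then states that "the sample size should be increased by 15% to preserve study power coupled with a 4% increase" for losses: 290 × 1.15 × 1.04 = 346.8 (345.1 if the two percentages are added), against 350. The figures reproduce. The SD of 9 is unadjusted, so the plan takes no credit for any covariate.

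**Step 2: effect of adding SAPS 3, linear approximation.**

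- Standard error at 350 = 9 × √(4/350) × √(1 − R²)
- Extra patients = 350/(1 − R²) − 350
- Power from a nominal 80% = Φ(2.802/√(1 − R²) − 1.960)

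| Assumed partial R² | SE (days) | Reduction in SE | 95% CI half-width (days) | Equivalent extra patients | Power from 80% |
|---|---|---|---|---|---|
| 0 | 0.962 | 0% | 1.89 | 0 | 80.0% |
| 0.02 | 0.952 | 1.0% | 1.87 | 7 | 80.8% |
| 0.05 | 0.938 | 2.5% | 1.84 | 18 | 82.0% |
| 0.10 | 0.913 | 5.1% | 1.79 | 39 | 84.0% |

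The last column treats the 15% and 4% allowances as used up. If they are not, 350 patients with SD 9 give 87.7% power, rising to 89.2% at R² = 0.05 and 90.8% at 0.10.

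**Step 3: overlap with covariates already in the model.** Partial R² = (R² full − R² base)/(1 − R² base). Assume correlations with VFD of −0.25 for age, 0.20 for PaO₂/FiO₂ and −0.30 for SAPS 3, with age and PaO₂/FiO₂ uncorrelated. Then R² base = 0.0625 + 0.04 = 0.1025.

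- SAPS 3 unrelated to both: R² full 0.193, partial R² 0.100, SE cut 5.1%.
- SAPS 3 correlated 0.3 with age and −0.2 with PaO₂/FiO₂: R² full 0.142, partial R² 0.044, SE cut 2.2%.
- SAPS 3 correlated 0.5 and −0.3: R² full 0.123, partial R² 0.022, SE cut 1.1%.

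If the SAPS 3 correlation with VFD is only −0.20, the last case gives no gain.

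**Step 4: the same variance seen as chance imbalance.** With 175 per arm, the standardized difference in a baseline score has SD √(2/175) = 0.107. A difference of at least 0.2 SD therefore occurs in about 6% of trials. It would move the unadjusted estimate by 0.2 × √R² × 9, which is 0.4 days at R² = 0.05 and 0.6 days at R² = 0.10, against a target of 3 days. This restates Step 2 and must not be added to it.

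**The case against.** The strongest reply is that this is a choice of covariates and nothing is broken. The set is pre-specified and identical in all three documents. The sample size does not lean on adjustment. Chance imbalance is already covered by the confidence interval and the type I error, and Table 1S will show any imbalance in SAPS 3. All of that stands.

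The size of the gain is also open. It rests wholly on an assumed R², and the formula belongs to a linear model, whereas the plan is a beta-type mixed model. That stands too, and is why the range starts at zero.

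A reader might infer that the precision is free, at the price of one degree of freedom. The documents do not support that. A zero/one inflated model has several components, and the plan does not say which carry the covariates, so one score could need several parameters in a model with 51 centers averaging about 7 patients (350/51). Multiple imputation is specified for the primary outcome only, so a missing SAPS 3 value needs a new rule. Planned collection for everyone is not proof of completeness.

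Last, changing the primary model during an open-label trial that has already enrolled at least 182 patients carries a credibility cost, and amendments need approval from the national ethics committee. This is a reason to document the change carefully. It does not rule the change out, because the choice can be made without arm-level results. The SAP also already plans to fit the main model with SAPS 3 in it, as an interaction, so feasibility and missing values have to be faced in any case.

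**Conclusion.** The point holds as an optional, low-cost improvement. The primary model omits a baseline severity score planned for all patients, on an endpoint partly driven by death. For an assumed partial R² of 0 to 0.10 and a linear approximation, adding the score cuts the standard error by 0 to 5%, equal to 0 to 39 patients on 350, or 80% power becoming 80 to 84%. Heavy overlap with age and PaO₂/FiO₂ would put the gain near the bottom of that range. For scale, the plan's own 4% allowance for losses is about 12 patients on 290, and a partial R² of 0.03 is worth about 11.

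A reader might go further and infer that the primary comparison is biased or the trial underpowered without SAPS 3. Neither follows. Leaving a prognostic covariate out of a randomized comparison costs at most precision, and the stated sample size reproduces from an unadjusted SD.

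**What to change.** Before database lock, add baseline SAPS 3 as a continuous covariate to the primary model wherever it is described: protocol Statistical methods, the SAP, and the DMC charter. Keep the three present covariates and the random center effect. State a simple single-imputation rule for missing SAPS 3, for example the overall median taken without regard to arm. If the zero/one inflated form is used, say which components carry the covariates. Report the marginal mean difference in days as planned, since that is the scale on which the precision gain is wanted.

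The decision should be made without access to arm-level results, and the amendment should record this. It matters here because the trial is open-label and steering committee members may have database access.

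The cost is a few words in three documents, a dated and approved amendment, the missing-value rule, and one extra term (or one per component), with little return if SAPS 3 largely repeats age and oxygenation. If the sponsor prefers not to alter the primary model at this stage, the smaller step is to give the reason for the covariate set and pre-specify a sensitivity analysis adjusted for continuous SAPS 3.
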